3.3.1 Inclusion Criteria

1. Histopathological proven prostate adenocarcinoma.
2. Rising PSA after definitive therapy with prostatectomy or radiation therapy (external beam or brachytherapy).

- a. Post radical prostatectomy (RP) – AUA recommendation
 - i. PSA greater than 0.2 ng/mL measured more than 6 weeks after RP and,
 - ii. Confirmatory persistent PSA greater than 0.2 ng/mL
- b. Post-radiation therapy –ASTRO-Phoenix consensus definition
 - i. Nadir + greater than or equal to 2 ng/mL rise in PSA
3. Karnofsky performance status of ≥ 50 (or ECOG/WHO equivalent).
4. Age > 18.
5. Ability to understand a written informed consent document, and the willingness to sign it.

3.3.2 Exclusion Criteria

1. Investigational therapy for prostate cancer.
2. Unable to lie flat, still or tolerate a PET scan.
3. Prior history of any other malignancy within the last 2 years, other than skin basal cell or cutaneous superficial squamous cell carcinoma that has not metastasized and superficial bladder cancer.
4. Contraindication to furosemide administration including prior allergy or adverse reaction to furosemide or sulfa drugs. (Note: This exclusion criteria can be removed if Furosemide is omitted as part of the PET imaging protocol if a second-generation scatter correction is available for the used PET device).

3.4 Duration of Follow Up

Patients will be followed for one day after the administration of the radiopharmaceutical.

3.5 Study Timeline

3.5.1 Primary Completion

The study will reach primary completion 36 months from the time the study opens to accrual.

3.5.2 Study Completion

The study will reach study completion 48 months from the time the study opens to accrual.

4 Study Drugs

4.1 Description, Supply and Storage of Investigational Drugs

4.1.1 Investigational Drug #1

Ga-68 labeled PSMA-11 (or PSMA-HBED-CC) is a radiopharmaceutical that will be produced under cGMP by a research pharmacists certified and highly experienced in the Department of Radiology and Biomedical Engineering, [REDACTED]. The radiopharmaceutical will be made at the China Basin Imaging Center. Imaging will occur at both the China Basin Imaging Center and the San Francisco VA Medical Center.

5 Treatment Plan

5.1 Dosage and Administration

The imaging agent (Ga-68 PSMA-11 or PSMA-HBED-CC) will be administered on an outpatient basis. It will be administered a single time intravenously prior to the PET imaging. The one-time nominal injected dose will be 3 to 7 mCi of ⁶⁸Ga-PSMA-11.

5.1.1 Other Modality(ies) or Procedures

5.1.1.1 Change in management surveys

Referring clinicians will be required to fill out a pre-imaging survey within 30 days of imaging. Please see Appendix 3. Additionally within 30 days of the completion of imaging, the referring physician will be requested to fill out a post-imaging survey, and finally six months after imaging, a third survey will be filled out.

5.1.1.2 PET imaging

a) ⁶⁸Ga-PSMA-11 PET preparation and injection:

The injected dose will be 111-259 MBq (3-7 mCi) of ⁶⁸Ga-PSMA-11 PET. A dose of 20 mg of Furosemide (Lasix) is recommended to be injected together with, shortly before or after administration of the radiotracer in order to minimize PET scatter artifacts from excreted radiotracer accumulation in the kidney and urinary bladder that can occur with the gallium-68 radionuclide. Oral hydration and voiding is recommended immediately before start of the scan. Furosemide should not be administered in patients with medical contraindications to Furosemide administration including allergies and adverse reactions including sulfa allergies. (Note: Application of Furosemide can be omitted as part of the PET imaging protocol if a second-generation scatter correction algorithm is available for the PET scanner used in this protocol). PET imaging will begin 50-100 minutes after injection. Scan time per bed position will be determined based on each sites PET scanner capabilities.

b) Patient preparation: no fasting is required.

c) PET protocol: Scan coverage will extend from mid thigh to the base of the skull, starting from the mid-thighs to prevent urinary bladder radiotracer accumulation at the start of PET imaging. Bed position scan time will be dependent on each sites scanner capabilities. At a minimum, 3 minutes per bed position will be used. In certain circumstances, coverage may be extended to the toes. Contrast may be administered if requested by the referring clinician and is decided site dependent.

d) Patient monitoring: Vital signs will be assessed immediately before and after injection of ⁶⁸Ga-PSMA-11 (HR and supine BP). Patients will be monitored for adverse events during injection and for two hours after radiotracer administration. Additionally, patient's vitals (HR and supine BP) will be checked at the completion of the imaging study prior to leaving the imaging center.

e) Patient follow-up: Patients will be contacted by phone one to three days after ⁶⁸Ga-PSMA-11 PET to assess for the development of delayed adverse events. Patients will be seen in the clinic if there are any concerning study related adverse events requiring further evaluation.

5.2 Monitoring and Toxicity Management

Each patient receiving Ga-68 PSMA-11 will be evaluable for safety. The safety parameters include physical findings and spontaneous reports of adverse events reported to the investigator by patients.

6 Study Procedures and Observations

6.1 Schedule of Procedures and Observations

Screening assessments must be performed within 30 days prior to the first dose of investigational product. Any results falling outside of the reference ranges may be repeated at the discretion of the investigator. Treatment or visit delays for public holidays or weather conditions do not constitute a protocol violation.

A written, signed, informed consent form (ICF) and a Health Insurance Portability and Accountability Act (HIPAA) authorization must be obtained before any study-specific assessments are initiated. A copy of the signed ICF will be given to the subject and a copy will be filed in the medical record. The original will be kept on file with the study records.

Period/ Procedure	Screening	Imaging day 1	One day post imaging	Follow-up surveys
Study Day/Visit Day	-30 to 1	1	2	2 to 30 days and six months
Informed consent	X			
Laboratory values, history from medical record	X			
Pre-survey	X			
Performance status	X			
Blood Pressure, HR	X	X		
Imaging Procedure				
⁶⁸ Ga-PSMA-11		X		
PET/CT or PET/MRI		X		
Follow-up				
Adverse event reporting			X	
Post-survey				XX

6.1.1.1 Screening Assessments

The Screening procedures and assessments must be completed within 30 days of the day 1 Visit.

- Laboratory values: all patients must have a recent PSA (within 30 days prior to study enrollment) consistent with BCR

- Pathology: all patients must have histopathology/biopsy of the prostate with a documented Gleason score
- Performance status: all patients must have their Karnofsky performance status (or ECOG/WHO equivalent) evaluated (Appendix A).

6.1.2 Treatment Period

6.1.2.1 Study Procedures, Imaging Day 1

- Vital signs
- Evaluation of adverse events

6.1.3 Post-treatment Follow Up Visits

Patients will be followed for two weeks after enrollment, by phone. The following procedure will be performed at two weeks:

- Evaluation of adverse events

6.2 Prohibited Medications

There are no prohibited medications.

7 Reporting and Documentation of Results

7.1 Evaluation of Efficacy (or Activity)

7.1.1.1 Definitions

Evaluable for toxicity

All patients will be evaluable for toxicity from the time of ^{68}Ga -PSMA-11.

7.2 Evaluation of Safety

Analyses will be performed for all patients receiving ^{68}Ga -PSMA-11. The study will use the [CTCAE v4.0](#) for reporting of adverse events.

7.3 Definitions of Adverse Events

7.3.1 Adverse Event

An adverse event (also known as an adverse experience) is defined as any untoward medical occurrence associated with the use of a drug in humans, whether or not considered drug related. More specifically, an adverse event (can be any unfavorable and unintended sign (e.g., an abnormal laboratory finding), symptom, or disease temporally associated with the use of a drug, without any judgment about causality. An adverse event can arise from any use of the drug (e.g., off-label use, use in combination with another drug) and from any route of administration, formulation, or dose, including an overdose.

7.3.2 Adverse reaction

An adverse reaction is defined as any adverse event caused by the use of a drug. Adverse reactions are a subset of all suspected adverse reactions for which there is reason to conclude that the drug caused the event.

7.3.2.1 Suspected

A suspected adverse reaction is defined as any adverse event for which there is a reasonable possibility that the drug caused the adverse event. For the purposes of IND safety reporting, “reasonable possibility” indicates that there is evidence to suggest a causal relationship between the drug and the adverse event. A suspected adverse reaction implies a lesser degree of certainty about causality than an adverse reaction.

7.3.2.2 Unexpected

An adverse event or suspected adverse reaction is considered *unexpected* if it is not listed in the investigator brochure or package insert(s), or is not listed at the specificity or severity that has been observed, or, if an investigator brochure is not required or available, is not consistent with the risk information described in the general investigational plan or elsewhere in the current application.

“Unexpected,” as used in this definition, also refers to adverse events or suspected adverse reactions that are mentioned in the investigator brochure as occurring with a class of drugs or

as anticipated from the pharmacological properties of the drug, but are not specifically mentioned as occurring with the particular drug under investigation.

Adverse events that would be anticipated to occur as part of the disease process are considered *unexpected* for the purposes of reporting because they would not be listed in the investigator brochure. For example, a certain number of non-acute deaths in a cancer trial would be anticipated as an outcome of the underlying disease, but such deaths would generally not be listed as a suspected adverse reaction in the investigator brochure.

7.3.2.3 Serious

An adverse event or suspected adverse reaction is considered *serious* if, in the view of either the investigator or sponsor, it results in any of the following outcomes:

- Death
- Life-threatening adverse event
- Inpatient hospitalization or prolongation of existing hospitalization
- A persistent or significant incapacity or substantial disruption of the ability to conduct normal life function
- Congenital anomaly/birth defect

Important medical events that may not result in death, are life-threatening, or require hospitalization may be considered serious when, based upon appropriate medical judgment, they may jeopardize the patient or subject and may require medical or surgical intervention to prevent one of the outcomes listed in this definition. Examples of such medical events include allergic bronchospasm requiring intensive treatment in an emergency room or at home, blood dyscrasias or convulsions that do not result in inpatient hospitalization, or the development of drug dependency or drug abuse.

7.3.2.4 Life-threatening

An adverse event or suspected adverse reaction is considered *life-threatening* if, in the view of either the investigator or sponsor, its occurrence places the patient or subject at immediate risk of death. It does not include an adverse event or suspected adverse reaction that, had it occurred in a more severe form, might have caused death.

7.4 Recording of an Adverse Event

All grade 3 and above adverse events will be recorded using the NCI CTCAE v4.0. The Investigator will assign attribution of the possible association of the event with use of the investigational drug.

Relationship	Attribution	Description
Unrelated to investigational drug/intervention	Unrelated	The AE is clearly NOT related to the intervention
	Unlikely	The AE is doubtfully related to the intervention
Related to investigational drug/intervention	Possible	The AE may be related to the intervention
	Probable	The AE is likely related to the intervention
	Definite	The AE is clearly related to the intervention

Signs or symptoms reported as adverse events will be graded and recorded by the Investigator according to the CTCAE. When specific adverse events are not listed in the CTCAE they will be graded by the Investigator as *none*, *mild*, *moderate* or *severe* according to the following grades and definitions:

- Grade 0 No AE (or within normal limits)
- Grade 1 Mild; asymptomatic or mild symptoms; clinical or diagnostic observations only; intervention not indicated
- Grade 2 Moderate; minimal, local, or noninvasive intervention (e.g., packing, cautery) indicated; limiting age-appropriate instrumental activities of daily living (ADL)
- Grade 3: Severe or medically significant but not immediately life-threatening; hospitalization or prolongation of hospitalization indicated; disabling; limiting self-care ADL
- Grade 4: Life-threatening consequences; urgent intervention indicated
- Grade 5: Death related to AE

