2.3.2 Secondary endpoints

- Per patient and per region detection sensitivity using a combined histology and conventional imaging correlate
- Sensitivity, specificity and negative predictive value on a per-patient basis.
- Change in management: survey based results
- Inter-reader reproducibility
- Safety: blood pressure, heart rate, self reported adverse events

3 Study Design

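### Section 7.4 is inconsistent on the lowest grade of adverse event to be recorded, and its grade 3 threshold does not fit the safety endpoint

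*Combined protocol and SAP*

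**What the plan says.** Section 7.4 contains two recording rules. The first is its opening sentence: "All grade 3 and above adverse events will be recorded using the NCI CTCAE v4.0". The second comes after the attribution table: "Signs or symptoms reported as adverse events will be graded and recorded by the Investigator according to the CTCAE". The second rule has no minimum grade. For events that CTCAE does not list, the section then supplies a severity scale that includes "Grade 1 Mild; asymptomatic or mild symptoms; clinical or diagnostic observations only; intervention not indicated" and "Grade 2 Moderate; minimal, local, or noninvasive intervention".

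The secondary endpoint in 2.3.2 reads "Safety: blood pressure, heart rate, self reported adverse events". Section 5.2 describes what is collected: "The safety parameters include physical findings and spontaneous reports of adverse events reported to the investigator by patients". Section 7.2 sets the safety population ("Analyses will be performed for all patients receiving" the agent) and names CTCAE v4.0 for adverse-event reporting. Section 7.3.1 defines an adverse event as "any untoward medical occurrence associated with the use of a drug in humans, whether or not considered drug related". Section 7.5 requires follow-up of all adverse events until they resolve. None of these sections limits the events by grade.

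**The concern.** A sentence that names a minimum grade, placed first in the section on recording, reads naturally as a threshold. If every grade were meant, naming grade 3 would do no work. A coordinator who applies that sentence alone would not enter a mild or moderate event that a patient reports by phone. The endpoint in 2.3.2 would count that event.

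Sections 1.1, 3.1 and 3.2 describe a multi-center study, a target of 1,500 patients across sites, and data shared between institutions for a pooled new drug application. If sites follow different sentences, a site with no mild events cannot be told apart from a site that did not record them. The loss may also be permanent. The safety contact is planned at one day (3.4), one to three days (5.1.1.2) or two weeks (6.1.3), so a mild event not written down then may not be recoverable later.

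Attribution may be affected too. The instruction to assign it directly follows the grade 3 sentence and refers back to the event named there. It is therefore unclear whether causality must be judged for lower grades.

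**Working it through.** The plan states no adverse-event count or rate, so there is no figure to reproduce. The check is a comparison of the text.

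**Step 1: the grade limit in each place.**

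| Section | Subject | Minimum grade |
|---|---|---|
| 2.3.2 | Safety endpoint | None |
| 5.2 | Safety parameters | None |
| 7.2 | Safety analyses, use of CTCAE | None |
| 7.3.1 | Definition of an adverse event | None |
| 7.4, opening sentence | Recording | Grade 3 |
| 7.4, later sentence | Grading and recording of reported signs or symptoms | None |
| 7.5 | Follow-up of adverse events | None |

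The opening sentence of 7.4 is the only place with a limit.

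**Step 2: whether the two sentences in 7.4 can be reconciled.** They cannot be separated by grading system, because both refer to CTCAE. The grade 1 and 2 definitions do not settle the matter alone: a site might grade an event simply to learn whether it reaches grade 3. The conflict lies in the later sentence, which says that reported signs or symptoms are recorded as well as graded.

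**Step 3: whether the analysis plan settles it.** Section 8.3.3 covers predictive values, sensitivity, specificity, detection rates and management impact. It describes no safety analysis, so it does not say which events would be counted.

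**Step 4: the effect on an all-grade rate.** Let p be the true proportion of patients whose worst event is grade 1 or 2, and f the share of patients at sites that record every grade. Assume p is the same at all sites. Then:

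- recorded proportion = f × p
- shortfall = (1 − f) × p

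With f = 1 nothing is lost. With f = 0 the recorded proportion is zero whatever p is. The documents give neither p nor f, so the shortfall cannot be given a number. Grade 3 and higher events are recorded under either sentence, so their rate does not depend on f.

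**The case against.** The strongest reply is that the text never says lower grades are to be left out. The opening sentence can be read as a floor: grade 3 and higher events are always captured, whatever their source, while signs or symptoms that patients report are captured at any grade under the later sentence. On that reading the self-reported endpoint is complete, and nearly every other safety section points the same way. This reading is possible and should be granted. But the protocol does not state it, and each site would have to infer it. It would also leave open whether lower-grade findings that the patient did not report are recorded, although 5.2 counts physical findings among the safety parameters.

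Three stronger conclusions are tempting but not supported:

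- **A reader might infer that the plan records nothing below grade 3.** It does not say so. The loss of grade 1 and 2 events follows from one of two readings.
- **A reader might put a count on the loss.** An assumed rate of 1% to 5% gives 15 to 75 patients among 1,500 (1,500 × 0.01 and 1,500 × 0.05), or about 4 to 19 among the 375 planned at UCSF (375 × 0.01 = 3.75; 375 × 0.05 = 18.75). The rate is not in the documents, and the count requires every site to take the strict reading. It is also not clear that this section governs all 1,500 patients: 1.1 speaks of aligned criteria and shared data, while 9.4 mentions participating sites.
- **A reader might infer that the safety data could not be pooled at all, or would be silent on milder effects.** Grade 3 and higher events can be pooled under either reading. Blood pressure and heart rate are collected separately around injection and at the end of imaging (5.1.1.2).

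**Conclusion.** The inconsistency is real and rests on the text alone. Section 7.4 gives two recording rules with different minimum grades, and the stricter one does not fit the endpoint in 2.3.2 or sections 5.2, 7.2, 7.3.1 and 7.5. A site that follows the opening sentence as written would omit grade 1 and 2 events. Sites that differ could not be validly combined for an all-grade rate.

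The consequence is conditional on how sites read the section, and its size cannot be derived from the documents. It affects a secondary safety endpoint and leaves the primary analysis of predictive value untouched. It is still worth correcting, because the data are meant to support a marketing application and the ambiguity is easy to remove before data are collected.

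**What to change.** Replace the opening sentence of 7.4 with: *All adverse events of any grade will be recorded and graded using the NCI CTCAE v4.0.* It would then agree with the later sentence in 7.4 and with 2.3.2, 5.2 and 7.2. The attribution instruction that follows would apply to every recorded event.

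Do not keep grade 3 and above as a separate reporting category. No reporting rule in 7.6 is based on grade 3: expedited reporting there turns on seriousness, unexpectedness and suspected causality, or on a related death. A grade-based category would be a new, undefined rule.

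The cost is slightly more case-report-form entry. The phone contact and the grading scale are already in the protocol.

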7.5 Follow-up of Adverse Events

All adverse events will be followed with appropriate medical management until resolved. Patients removed from study for unacceptable adverse events will be followed until resolution or stabilization of the adverse event. For selected adverse events for which administration of the investigational drug was stopped, a re-challenge of the subject with the investigational drug may be conducted if considered both safe and ethical by the Investigator.

7.6 Expedited Reporting

Reporting to the Data and Safety Monitoring Committee

If a death occurs during the treatment phase of the study or within 30 days after the last administration of the study drug(s) and it is determined to be related either to the study drug(s) or to a study procedure, the Investigator or his/her designee must notify the DSMC Chair (or qualified alternate) within 1 business day of knowledge of the event. The contact may be by phone or e-mail.

Reporting to UCSF Committee on Human Research (Institutional Review Board)

The Principal Investigator must report events meeting the UCSF CHR definition of "Unanticipated Problem" (UP) and the San Francisco VA Medical Center within 5 business days of his/her awareness of the event.

Expedited Reporting to the Food and Drug Administration

If the study is being conducted under an IND, the Sponsor-Investigator is responsible for determining whether or not the suspected adverse reaction meets the criteria for expedited reporting in accordance with Federal Regulations (21 CFR §312.32).

The Investigator must report in an IND safety report any suspected adverse reaction that is both serious and unexpected. The Sponsor-Investigator needs to ensure that the event meets all three definitions:

- Suspected adverse reaction (as defined in 6.1.30)
- Unexpected (as defined in 0)
- Serious (as defined in 6.1.5)

If the adverse event does not meet all three of the definitions, it should not be submitted as an expedited IND safety report.

The timeline for submitting an IND safety report to FDA is no later than **15 calendar days** after the Investigator determines that the suspected adverse reaction qualifies for reporting (21 CFR 312.32(c)(1)).

Any unexpected fatal or life-threatening suspected adverse reaction will be reported to FDA no later than **7 calendar days** after the Investigator's initial receipt of the information (21 CFR 312.32(c)(2)).

Any relevant additional information that pertains to a previously submitted IND safety report will be submitted to FDA as a Follow-up IND Safety Report without delay, as soon as the information is available (21 CFR 312.32(d)(2)).

8 Statistical Considerations and Evaluation of Results

